2.2.2 Secondary Endpoints

- Objective response rate (ORR) as determined by the proportion of subjects with either complete response or partial response, as defined by RECIST 1.1, at 8 weeks, 16 weeks, and 24 weeks following initiation of FOLFOX-nal-IRI.
- Stable disease rate (SDR) as determined by the proportion of subjects with no progression of disease as defined by RECIST 1.1, at 8 weeks, 16 weeks, and 24 weeks following initiation of FOLFOX-nal-IRI.
- Rate of resectability as determined by the proportion of subjects who undergo surgical resection of tumors.
- The serum levels of CA 19-9 prior to initiation of chemotherapy and after every 2 cycles (every 4 weeks) following initiation of FOLFOX-nal-IRI.
- Progression-free survival (PFS) as determined by the time interval from the date of first dose of study drug to first documented disease progression or death from any cause, whichever occurs first, if evaluable.
- Overall survival (OS) as defined as the time interval from the date of the first dose of study drug to date of death from any cause.
- Safety and tolerability of FOLFOX-nal-IRI; Grade 3 and 4 toxicities as defined by the NCI Common Terminology Criteria for Adverse Events (NCI CTCAE) v5.
- Quality of life as measured at baseline and after every 4 cycles (every 8 weeks) using the European Organization for Research and Treatment of Cancer Quality-of-Life Core Questionnaire (EORTC-QLQ-C30).

2.2.3 Exploratory Endpoints

- Effect of FOLFOX-nal-IRI DNA damage and apoptosis, in biopsied and surgically
 resected tumor tissue specimens (for subjects who undergo surgical resection of tumors),
 as determined by immunohistochemistry (or ELISA) for DNA damage/repair
 (phosphorylated histone H2AX, γH2AX), DNA double strand damage response (p53
 binding protein, 53BP1), apoptosis (activated caspase 8 and caspase 3).
- Effect of treatment-induced DNA damage and apoptosis in peripheral blood lymphocytes (PBLs) before treatment and following every 4 cycles (8 weeks) of treatment, as determined by yH2AX and 53BP1, and serum biomarkers for apoptosis.
- Molecular profiling as determined by next-generation sequencing of genomic (exon) DNA (*BRCA1*, *BRCA2*, *TP53*, *CDKN2A*, *KRAS*), and correlation with treatment response based on CT scans and serum CA 19-9.
- Metabolic profiles of plasma before treatment and following every 4 cycles (8 weeks) of treatment, as determined by liquid chromatography/tandem mass spectrometry (by metabolomics core facility).
- The inter-institutional variability of the overall resectability rate as determined by central imaging analysis of tumor involvement of regional vasculature.

3. ELIGIBILITY CRITERIA

3.1 Inclusion Criteria

Subject must meet all of the following applicable inclusion criteria to participate in this study:

- 1. Written informed consent and HIPAA authorization for release of personal health information. **NOTE:** HIPAA authorization may be included in the informed consent or obtained separately.
- 2. Age \geq 18 years at the time of consent.
- 3. ECOG Performance Status of 0-1 within 28 days prior to registration.
- 4. Histological or cytological confirmation of pancreatic carcinoma.
- 5. Measurable disease according to RECIST v1.1 within 28 days prior to registration.
- 6. Previously untreated pancreatic carcinoma considered as locally advanced unresectable according to NCCN guidelines.
- 7. Demonstrate adequate organ function as defined in the table below; all screening labs to be obtained **within 14 days** prior to initiation of study treatment.

System	Laboratory Value
Hematological	
Absolute Neutrophil Count (ANC)	\geq 1,500 /µL
Hemoglobin (Hgb)	≥ 8 g/dL with blood transfusion permitted
Platelet (Plt)	\geq 100,000 /µL
Renal	
Serum creatinine	\leq 1.5 × upper limit of normal (ULN) OR
Calculated creatinine clearance using	\geq 50 mL/min for subjects with creatinine levels >
the Cockcroft-Gault formula	1.5 ULN
Hepatic	
Total bilirubin	\leq 1.5 × ULN (biliary drainage is allowed for biliary
	obstruction). Patients with Gilbert's syndrome with
	a total bilirubin $\leq 3.0 \times$ ULN and direct bilirubin
	within normal limits are permitted.
Aspartate aminotransferase (AST)	$\leq 2.5 \times \text{ULN}$
Alanine aminotransferase (ALT)	$\leq 2.5 \times \text{ULN}$
Albumin	$\geq 3.0 \text{ g/dL}$
Coagulation	
International Normalized Ratio (INR)	\leq 1.5 × ULN unless subject is receiving
or Prothrombin Time (PT)	anticoagulant therapy, as long as PT, INR or PTT
Activated Partial Thromboplastin Time	is within therapeutic range of intended use of
(aPTT)	anticoagulants

8. Female subjects of childbearing potential must have a negative serum pregnancy test within 7 days of study registration and within 72 hours of Cycle 1 Day 1. **NOTE:** Female subjects are considered of childbearing potential unless they are surgically sterile (have undergone a

hysterectomy, bilateral tubal ligation, or bilateral oophorectomy) or they are naturally postmenopausal for at least 12 consecutive months.

- 9. Female subjects of childbearing potential and males must be willing to abstain from behaviors that could lead to pregnancy (heterosexual activity, sperm donation, in vitro fertilization, etc.) or to use 2 forms of effective methods of contraception from the time of informed consent until 9 months (females) or 6 months (males) after treatment discontinuation. The two contraception methods can be comprised of two barrier methods, or a barrier method plus a hormonal method.
- 10. As determined by the enrolling physician or protocol designee, ability of the subject to understand and comply with study procedures for the entire length of the study. The subject should be able to understand the purpose and risks of the study and provide a signed and dated informed consent form.

3.2 Exclusion Criteria

Subjects meeting any of the criteria below may not participate in the study:

- 1. Known hypersensitivity to irinotecan liposome, other liposomal products, oxaliplatin, 5-fluorouracil, leucovorin, or any ingredients in those preparations.
- 2. Pre-existing peripheral neuropathy (Grade 3 or 4) during screening.
- 3. Major surgery within 4 weeks of starting treatment.
- 4. Active uncontrolled cardiac arrhythmia or congestive heart failure (class 3 or 4 as defined by the New York Heart Association Functional Classification); or history of myocardial infarction, unstable angina; or acute coronary syndrome within 6 months prior to enrollment.
- 5. Known history of human immunodeficiency virus (HIV), or hepatic cirrhosis caused by active infection with hepatitis B virus (HBV, as defined by HBsAg positivity or positive DNA). Testing is not required for study entry if there is no clinical suspicion. Note: hepatic cirrhosis caused by other factors (ex. alcoholic cirrhosis) may be considered on a case-by-case basis if, in the opinion of the treating investigator, the disease is unlikely to compromise the subject's safety or put the study outcomes at unnecessary risk.
- 6. Any medical condition, life-threatening illness, or organ dysfunction, which in the investigator's opinion, can compromise the subject's safety or put the study outcomes at unnecessary risk.
- 7. Uncontrolled active systemic infection.
- 8. Concomitant medications that are prohibited in this study and they cannot be switched to alternative medications.
- 9. Pregnant or breastfeeding (**NOTE:** breast milk cannot be stored for future use while the mother is being treated on study).
- 10. Known additional malignancy that is active and/or progressive requiring treatment within 2 years of screening for this study; exceptions include basal cell or squamous cell skin cancer, in situ cervical or bladder cancer, low-grade prostate cancer, or other cancer for which the subject has been disease-free for at least five years. Additional exceptions could be

considered if agreed by sponsor-investigator and site investigator assuming the disease is considered extremely unlikely to confound evaluation of disease status.

11. Treatment with any investigational drug within 30 days prior to registration, or within a time interval less than at least 5 half-lives of the investigational agent, whichever is longer, prior to the first scheduled day of dosing of this study.

4. SUBJECT REGISTRATION

All subjects must be registered through Big Ten Cancer Research Consortium (Big Ten CRC) Administrative Headquarters'(AHQ) electronic data capture (EDC) system. A subject is considered registered when an 'On Study' date is entered into the EDC system. Subjects must be registered prior to starting protocol therapy and begin therapy **within 5 business days** of registration.

5. TREATMENT PLAN

This is a phase II, single-arm, open-label, clinical study to investigate the efficacy and tolerability of a combination of liposomal irinotecan (nal-IRI) with oxaliplatin, leucovorin, and 5-fluorouracil (FOLFOX-nal-IRI) for treatment of patients with locally advanced pancreatic carcinoma (LAPC). Each subject will be screened for eligibility and if eligible will be registered to the study. Within 28 days of screening, the consented subjects will have a central venous access device placed and then start treatment.

Subjects will receive FOLFOX-nal-IRI every 2 weeks as described below. Tumor response/surgical assessment will be evaluated after every 4 cycles of treatment with contrastenhanced CT scans using RECIST 1.1 criteria. If the tumor becomes surgically resectable and the subject is a surgical candidate as determined by a multidisciplinary team at any point, the subject should be removed from study treatment and undergo surgery (at which point he/she would enter survival follow-up). If the tumor remains unresectable and there is no tumor progression, each subject will be treated up to a total of 12 cycles of FOLFOX-nal-IRI. Oxaliplatin could be discontinued for Grade 3 or 4 neuropathy, and the subject would still be considered on study.

Following treatment with 12 cycles of FOLFOX-nal-IRI (for those patients not offered radiotherapy), if the tumor remains unresectable, the subjects may receive further treatment (chemotherapy using the same regimen or of the treating physician's choice, or chemoradiation therapy) or observation as determined by the treating physician. Regardless of choice at this point, patients should be followed for survival.

5.1 **Pre-medication and Hydration**

Premedication and hydration will be provided as per institutional standards. It should be noted that the regimen is considered moderately emetogenic. A corticosteroid and anti-emetic will be administered at least 30 minutes prior to infusion of nal-IRI and oxaliplatin or as per institutional standards.

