9: Research Blood Samples will be collected prior to treatment on Cycle 1 Day 1 then after every 2 cycles (every 4 weeks) starting at Cycle 3 Day 1 of FOLFOX-nal-IRI and at the safety follow up visit. These samples will be used for correlative testing as described in Section 8. See CLM for collection, processing, labeling and shipping instructions.

10: Whole blood for banking is to be collected at Pre-Treatment Cycle 1 Day 1. See CLM for collection, processing, labeling and shipping instructions.

11: Submission of unstained slides for banking from an archived FFPE tumor block (if available). See CLM for collection, labeling, and shipping instructions.

12: Serum and plasma for banking are to be collected at Pre-Treatment Cycle 1 Day 1 and at the 30-Day Safety Follow up visit. See CLM for collection, labeling, processing, and shipping instructions.

13: If screening (baseline) labs were performed within 7 days of Cycle 1 Day 1 of treatment, these do not need to be repeated.

14: When subjects permanently stop study treatment for whatever reason, a safety follow-up visit will occur 30 days (+7 days) after the last dose of treatment or before the initiation of a new anti-cancer treatment, whichever comes first.

15: Subjects without documented disease progression will be followed for disease progression every 3 months for 1 year from Day 30 visit. Once disease progression is documented, subjects will enter a survival follow up period every 3 months from the time of documented progression until death or lost to follow up. This follow up may be accomplished via phone call, email, telehealth, or communication with a local physician.

16: All CT/MRI images obtained throughout the study will be submitted for central analysis at the end of the study.

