7.2 Long Term Follow-up Evaluations

Subjects without documented disease progression will be followed for disease progression every 3 months for 1 year from day 30 visit. Once disease progression is documented, subjects will enter a survival follow up period every 3 months from the time of documented progression until death or lost to follow up. This follow up may be accomplished via phone call, email, telehealth, or communication with a local physician.

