12.2.2 Definition of Secondary Endpoints

- Objective response rate (ORR) as determined by the proportion of subjects with either complete response or partial response as defined by RECIST 1.1 at 8 weeks, 16 weeks, and 24 weeks following initiation of FOLFOX-nal-IRI.
- Stable disease rate (SDR) as determined by the proportion of subjects with no progression of disease as defined by RECIST 1.1, at 8 weeks, 16 weeks, and 24 weeks following initiation of FOLFOX-nal-IRI.
- Rate of resectability as determined by the proportion of subjects who undergo surgical resection of tumors.
- The serum levels of CA 19-9 prior to initiation of chemotherapy and after every 2 cycles (every 4 weeks) following initiation of FOLFOX-nal-IRI.
- Progression-free survival (PFS) as determined by the time interval from the date of first dose of study drug to first documented disease progression or death from any cause, whichever occurs first, if evaluable.
- Overall survival (OS) as defined as the time interval from the date of the first dose of study drug to date of death from any cause.
- Safety and tolerability of FOLFOX-nal-IRI; Grade 3 and 4 toxicities as defined by the NCI Common Terminology Criteria for Adverse Events (NCI CTCAE) v5.

• Quality of life as measured at baseline and after every 4 cycles (every 8 weeks) using the European Organization for Research and Treatment of Cancer Quality-of-Life Core Questionnaire (EORTC-QLQ-C30).

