12.6.2 Analysis Plans for Secondary Objectives

The Secondary Objectives will be analyzed as described in the section 12.2.2, Definition of Secondary Endpoints.

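### Section 5 puts resected (and still-unresectable) subjects into survival follow-up, while 7.2 follows everyone without progression for progression first, so PFS collection after treatment depends on which text a site follows

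*Combined protocol and SAP*

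**What the plan says.** Section 5 (Treatment Plan) takes a subject whose tumour becomes resectable off study treatment for surgery, "at which point he/she would enter survival follow-up". The synopsis carries the same rule. Section 5 also says that subjects still unresectable after 12 cycles are to be followed for survival whatever treatment comes next. It does not mention progression there.

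Section 7.2 sets a different order: "Subjects without documented disease progression will be followed for disease progression every 3 months for 1 year from day 30 visit". It continues: "Once disease progression is documented, subjects will enter a survival follow up period every 3 months from the time of documented progression". Footnote 15 of the study calendar repeats both sentences. Neither place makes an exception for resected subjects or for those who complete 12 cycles. On method, 7.2 adds: "This follow up may be accomplished via phone call, email, telehealth, or communication with a local physician".

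Section 12.2.2 defines PFS as the "time interval from the date of first dose of study drug to first documented disease progression or death from any cause", qualified only by the words if evaluable. Section 12.6.2 gives no further rule: "The Secondary Objectives will be analyzed as described in the section 12.2.2, Definition of Secondary Endpoints".

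**The concern.** A subject who is resected without having progressed falls under two rules. Section 5 sends that subject to survival follow-up at surgery. Section 7.2 keeps the same subject in progression follow-up for a year first. Since 7.2 uses survival follow-up for the phase after progression, a site reading Section 5 could reasonably collect vital status only. Two sites could handle identical subjects differently, and both would be within the protocol.

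What is at stake is PFS, a stated secondary endpoint. If recurrence is not collected, the analyst has two options for a resected subject. One is to wait for death, so that PFS becomes OS for that subject. The other is to censor at surgery, an event that may be related to prognosis. For an unresected subject who completed 12 cycles, the same literal reading leaves death or censoring at the last scan. The endpoint and analysis sections do not say which applies.

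**Working it through.** **Step 1: the texts side by side.**

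| Subject without documented progression | Section 5 | Section 7.2 and footnote 15 |
|---|---|---|
| Resected | Survival follow-up from surgery | Progression follow-up for 1 year, then survival |
| Unresectable after 12 cycles | Survival follow-up | Progression follow-up for 1 year, then survival |

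The conflict covers both groups.

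**Step 2: does the analysis text settle it?** It does not. The PFS definition has no censoring rule and does not mention surgery. It names progression only, whereas the ORR and DCR definitions in 9.8.3 and 9.8.4 add recurrence. Section 12.6.2 points back to the definition. Under calendar footnote 7, scheduled scans are tied to treatment cycles and imaging at discontinuation is discretionary, so Section 5 alone gives no route by which a later recurrence is documented.

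**Step 3: how long does 7.2 look for progression?** Assume no delays and 14-day cycles.
- Last dose in cycle 4: 42 + 30 + 365 = 437 days from first dose, about 14.4 months.
- Last dose in cycle 12: 154 + 30 + 365 = 549 days, about 18.0 months.

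The 7.2 route therefore captures progression to about 14 to 18 months.

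**Step 4: could the choice of rule matter?** The documents give no PFS median and no resection rate, so there is no figure to reproduce. The following is an illustration on assumed inputs: surgery at month 5 in 10-40% of subjects, all of them progression-free until then; exponential times; median PFS 9 months if unresected; median 9 or 18 months from surgery to progression if resected; median 8 months from progression to death; data to 30 months. The results are Kaplan-Meier medians from 200,000 simulated subjects, in months.

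| Resected | Post-surgery median | Followed for progression | Censored at surgery | Resected counted at death only |
|---|---|---|---|---|
| 10% | 9 | 9.6 | 9.6 | 10.3 |
| 10% | 18 | 10.0 | 9.6 | 10.4 |
| 20% | 9 | 10.1 | 10.1 | 11.8 |
| 20% | 18 | 11.0 | 10.2 | 12.2 |
| 30% | 9 | 10.7 | 10.7 | 13.6 |
| 30% | 18 | 12.3 | 10.8 | 14.5 |
| 40% | 9 | 11.3 | 11.3 | 15.4 |
| 40% | 18 | 13.5 | 11.2 | 17.1 |

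Hand check at 30% resected. At month 5, S = 0.7 × 2^(−5/9) + 0.3 = 0.776. With censoring at surgery, S(t) = 0.776 × 2^(−(t−5)/9) afterwards, which reaches 0.5 at t = 5 + 9 × log2(0.776/0.5) = 10.7. With full follow-up and a 9-month post-surgery median the curve is the same, so censoring at surgery then costs nothing. With an 18-month post-surgery median and full follow-up, S(12.3) = 0.7 × 2^(−12.3/9) + 0.3 × 2^(−7.3/18) = 0.271 + 0.226 = 0.498, so the median is about 12.3.

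The spread between the rules is 10.4 − 9.6 = 0.8 months at 10% resected and 14.5 − 10.8 = 3.7 months at 30%, both with the 18-month post-surgery median. In subjects, 10% of the target of 28 is 2.8 and 30% is 8.4.

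**The case against.** The strongest reply is that 7.2 and footnote 15 are the dedicated follow-up rules and, on their plain wording, already cover resected subjects. Section 5 may be using survival follow-up as shorthand for all long-term follow-up. Its similar wording for unresected subjects supports that, because taken literally it would leave 7.2 little to do. This has force. It makes 7.2 the likelier intent, but a site still has to guess, and the synopsis repeats the resection rule.

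A reader might infer several stronger things that the documents do not support:
- **That PFS cannot be determined in resected subjects, or that they have no valid PFS time.** Deaths are captured under either text, and under 7.2 progression is sought for a year. What is unsettled is the follow-up and censoring rule.
- **That the gap falls only on the best responders.** Section 5 has the same looseness for unresected subjects after 12 cycles, and resectability is a multidisciplinary judgement, not a RECIST category.
- **That censoring at surgery must bias PFS.** It does so only if the hazards differ. With equal hazards the illustration shows no effect.
- **That the effect is large.** Section 1.1 describes down-staging to resectability as rare, so the upper end of the assumed range has no support in the documents.

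It is also fair to say that treating surgery as neither an event nor a reason for censoring is one defensible choice among several. The plan still needs to make a choice.

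**Conclusion.** The inconsistency is real and should be corrected. Section 5 and 7.2 with footnote 15 give different follow-up for subjects without documented progression, and nothing in the statistical section resolves it. Followed literally, Section 5 would leave PFS in these subjects to be counted at death, which lengthens it because death cannot precede progression, or censored at surgery, which is informative if resected subjects have a different hazard.

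The size cannot be stated from the documents. The illustration shows only that the rule can matter: under 1 month in the median at 10% resected and up to 3.7 months at 30%. These figures depend entirely on the assumed hazards, surgery time and resection rate, and on every site following Section 5 for resected subjects. They do not model loss of progression data in unresected subjects.

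PFS is secondary, with no threshold or comparator. The futility and success rules in 12.3 and 12.7 count responses, not PFS times, so the primary DCR decision does not rest on this point.

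**What to change.** 1. **Section 5, both sentences, and the synopsis.** State that subjects without documented progression, including those resected, enter the existing 7.2 follow-up for progression or recurrence, and move to survival follow-up afterwards. Name resected subjects in 7.2 and footnote 15 so that the texts agree.
2. **Data collection.** Record the date of recurrence or progression from whatever imaging is available, together with its source.
3. **Section 12.2.2, and the matching definition in 2.2.2.** State that documented recurrence after resection is a PFS event and that surgery alone is not an event. Report PFS censored at surgery as a sensitivity analysis.

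The cost is wording and one more data item for a few subjects, because the three-monthly contacts are already planned. Recurrence dates will stay imprecise: 7.2 sets no imaging schedule, allows remote contact, and stops looking for progression after one year. The report should say so.

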5.2 FOLFOX-nal-IRI Administration

The combination of 5-fluorouracil, leucovorin, and oxaliplatin (FOLFOX) used within the treatment regimen are part of standard of care drugs and they will be provided as per institutional standards.

	Drug/ Sequence	Dose ¹	Route ²	Schedule ³	Cycle Length
1	Oxaliplatin	60 mg/m^2	Intravenously (IV) over 2 hours (±15 min)	Day 1	
2	Liposomal Irinotecan (free base)	50 mg/m ²	IV over 90 minutes (±10 min) after completion of oxaliplatin	Day 1	14 days
3	Leucovorin	400 mg/m ²	IV over 30 minutes (±5 min) after completion of liposomal Irinotecan	Day 1	11 aays
4	5-Fluorouracil	2,400 mg/m ²	IV over 46 hours via infusion pump at home (±1 hr)	Day 1	

¹ Body surface area (BSA) should be recalculated when weight changes by $\geq 10\%$ according to the Mosteller formula.

² Drug administration times performed outside the above recommended windows will not be considered as protocol deviations.

³ A window of \pm 3 days may be applied to all study visits to accommodate observed holidays, inclement weather, scheduling conflicts etc. Date and time of each drug administration should be clearly documented in subject's chart and electronic case report forms (eCRFs).

